This is a multi-institution phase 1b/2 study of ATRA in combination with fixed dose Daratumumab, Pomalidomide and Dex for patients with relapsed multiple myeloma who have progressed on the combination of Dara + Len + Dex. During the dose escalation phase (phase 1b) and after the first cycle, patients who have not experienced a drug-limiting toxicity (DLT), have not shown signs of progressive disease (PD), and in the opinion of the investigator would continue to benefit from additional Dara + Pom + Dex + ATRA may receive additional cycles of treatment (see section 7.4 for details). The phase 2 portion will allow further enrollment at the maximum tolerated dose (MTD) to further evaluate safety and efficacy.

Study Population

Patients with relapsed or refractory multiple myeloma who have progressed on the combination of Dara + Len + Dex or Dara + Pom + Dex. We will include a maximum of 42 patients (among 20-32 subjects previously exposed to Dara + Len + Dex or 10-22 subjects previously exposed to Dara + Pom + Dex).

Length of Study

The overall study duration is expected to be three (3) years, two years for enrollment, one year to complete follow-up.

Treatment Plan

During 28-day treatment cycles, patients will receive Dara 1800 mg subcutaneous (SC) administration at their current dose upon enrollment onto the study depending on their cycle. (If they are on cycles 1-2

then they will receive Dara 1800 mg SC days 1,8,15,22; if they are on cycles 3-6 they will receive Dara 1800 mg SC days 1 and 15; if they are on cycle 7 or beyond they will receive Dara 1800 mg SC on day 1).

Pomalidomide will be administered at the patient's currently tolerated dose (4,3, or 2 mg po daily) on days 1-21. Patients who are progressing on daratumumab + lenalidomide + dexamethasone will start with the 4 mg dose (standard of care starting dose) of pomalidomide.

Dexamethasone will be administered at 40 mg once weekly on days 1,8,15 for patients 75 years old and younger and at 20 mg once weekly on days 1,8,15 for patients older than 75. Patients may stay on their currently administered steroid regimen if it does not match the above.

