3. STUDY ENDPOINTS

Primary Endpoints:

Phase 1b: The percentage of patients with treatment emergent adverse events (TEAEs) overall and per dose level.

- Patients with DLTs at each dose level.
- Patients with Grade ≥ 3 TEAEs
- Patient with serious adverse events (SAEs)
- Patients who discontinue because of TEAEs
- Patients with dose modifications (delays, interruptions, dose reductions)
- Clinically significant laboratory values

Phase 2: ORR as defined by IMWG criteria (subjects progressing on Dara + Len + Dex)

Secondary Endpoints:

- 1) ORR as defined by IMWG criteria (subjects progressing on Dara + Pom + Dex)
- 2) Rate of CR, sCR, or nCR
- 3) Rate of VGPR
- 4) TTP
- 5) DOR
- 6) PFS using Kaplan Meier
- 7) OS using Kaplan Meier

Exploratory Endpoints:

Explorative endpoints of samples collected before, during and after treatment with Dara + ATRA, + Pom + Dex and include but are not limited to the following:

- 1) Gut Microbiome analysis
- 2) Immune cell subset analyses
- 3) Analyses of cytokine, chemokine, inflammatory/anti-inflammatory and bacterial translocation markers
- 4) Basic peripheral blood laboratory variables
- 5) Genetic and epigenetic profiles

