4. OVERALL STUDY DESIGN

4.1. Study Design

This is a multicenter, open label study of Dara+Pom+Dex combined with ATRA in patients progressing on a Dara+Len+Dex regimen. The study is expected to enroll up-to a maximum of 42 patients (20-32 subjects previously exposed to Dara + Len + Dex; 10-22 subjects previously exposed to Dara + Pom + Dex)..

The phase 1b portion will follow a standard 3+3 dose escalation design with two dose levels and up to 12 patients. Under this design, the investigators will evaluate dose levels as follows:

- Dose level 1 - ATRA 35.5 mg/m²/day on days -2,-1 and 1 on a 28-day cycle in combination with daratumumab, pomalidomide, and dexamethasone
- Dose level 2 – ATRA 45 mg/m²/day on days -2,-1 and 1 on a 28-day cycle in combination with daratumumab, pomalidomide, and dexamethasone

During the dose-escalation phase and after the first cycle, and after the first cycle, patients who have not experienced a DLT, have not shown signs of PD, and in the opinion of the investigator would continue to benefit from treatment may receive additional cycles of treatment.

The phase 2 portion will be conducted in two stages. In the first stage, 10 patients will be accrued. A safety and efficacy analysis will be conducted 3 months after accrual of the first 10 patients. If there are 2 or fewer responses in these 10 patients, the study will be stopped due to futility. If the stopping rules for safety are met, then the study will be stopped due to toxicities. Otherwise, accrual will continue for a maximum of 42 in phase 1b and phase II combined.

During 28-day treatment cycles, patients will receive Dara 1800 mg subcutaneous (SC) at their current dose upon enrollment onto the study depending on their cycle. (If they are on cycles 1-2 then they will receive Dara 1800 mg SC days 1,8,15,22; if they are on cycles 3-6 they will receive Dara 1800 mg SC days 1 and 15; if they are on cycle 7 or beyond they will receive Dara 1800 mg SC on day 1).

Pomalidomide will be administered at the patient's currently tolerated dose (4,3, or 2 mg po daily) on days 1-21. For patients progressing on daratumumab, lenalidomide, and dexamethasone, the starting dose of pomalidomide will be 4 mg per standard of care.

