7.3. Definition of DLT

Toxicity will be evaluated according to the NCI CTCAE, Version 5.

Nonhematologic TEAEs of NCI CTCAE Grade ≥ 3 clearly unrelated to the underlying disease and occurring during the first cycle will be considered DLTs with the following exceptions:

- Asymptomatic laboratory changes (other than renal and hepatic laboratory values and Grade 4 lipase/amylase) that can be supplemented (reversion of Grade 4 events to Grade ≤ 2 , reversion of Grade 3 events to Grade ≤ 1 or baseline) within 72h.
- Grade 3 nausea/vomiting that can be managed subsequently with anti-emetics (Grade 3 nausea or vomiting that persists beyond 48h with or without appropriately medical intervention will be considered a DLT).
- Grade 3 fatigue lasting for <72 hours.
- Grade 3 elevation of ALT or AST that resolves to Grade ≤ 1 or baseline) within 7 days.

The following hematologic TEAEs of Grade ≥ 3 clearly unrelated to the underlying disease and occurring during the first cycle will be considered DLTs:

- Grade ≥ 3 hemolysis.
- Grade 4 neutropenia lasting more than 7 consecutive days.

- Grade 4 thrombocytopenia of any duration.
- Grade 3 thrombocytopenia with clinically significant bleeding.
- Any other Grade ≥ 4 hematologic toxicity with the following exception: Grade 4 lymphopenia

An incomplete recovery from treatment-related toxicity causing a >3 -week delay in the next scheduled infusion before the initiation of Cycle 2 will be considered a DLT.

For the purpose of dose escalation, DLTs are those events meeting the criteria above that occur before Cycle 2 Day 1 administration. Related TEAEs meeting DLT definitions occurring in later cycles or in Phase 2 (DLT-like events) will determine the suitability of the MTD dose for future studies.

Dose modifications for toxicity are described in Section 7.5.

Intrapatient dose escalation will be permitted only when patients in the next dose level cohort have completed assessments for Cycle 1 and a decision has been made that this dose level does not exceed the MTD. Eligible patients for intrapatient escalation can also be changed to a different schedule if the conditions described above are met (for example a Dose Level 1 patient could be moved to the last cleared dose level).

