Thrombocytopenia Grade 4 thrombocytopenia (Platelets $< 25,000/\mu\text{L}$)	Withhold the dose and follow CBC weekly. Dosing may resume at one dose level lower once the platelet count has recovered to $\geq 50,000/\mu\text{L}$.
Rash, Grade 3	Withhold dose for remainder of cycle. Decrease by one dose level when dosing restarted at next cycle (rash must resolve to \leq Grade 1 before restarting dosing).
Rash, Grade 4 or Blistering	Discontinue subject from study treatment.
VTE \geq Grade 3	Withhold dose for remainder of cycle. Assess anticoagulation treatment. Maintain dose level when dosing restarted at next cycle at discretion of treating physician. For Grade 4 VTE, discontinue pomalidomide treatment.
Other \geq Grade 3 POM-related ^b adverse events	Withhold dose. Decrease by one dose level when dosing restarted (adverse event must resolve to \leq Grade 1 before restarting dosing). For Grade 4 non-hematologic adverse events, discontinue pomalidomide treatment.

ANC = absolute neutrophil count; GCSF = granulocyte colony-stimulating factor; POM = Pomalidomide; VTE = venous thromboembolism.

^a If recovery from toxicities is prolonged beyond 14 days, then the dose of POM will be decreased by one dose level when dosing is restarted.

^b For Grade 3 or 4 AEs that are not considered to be related to study drug, the treating physician should consult with the sponsor institution for dose interruptions and reductions.

Table 5: Pomalidomide Dose Reduction Steps

Dose Level ^a	Pom Dose reduction
Starting dose	4 mg
Dose Level -1	3 mg
Dose Level -2	2 mg
Dose Level -3	1 mg

^a The minimum permitted dose level for POM is 1.0 mg. No dose re-escalation is permitted for Pomalidomide.

Table 6: Dose Reductions for Dexamethasone-related Toxicities

Toxicity ^a	Dex Dose Modification
Dyspepsia = Grade 1-2	Maintain dose and treat with histamine (H2) blockers or equivalent. Decrease by one dose level if symptoms persist.

Dyspepsia \geq Grade 3	Withhold dose until symptoms are controlled. Add H2 blocker or equivalent and decrease one dose level when dose restarted.
Edema \geq Grade 3	Use diuretics as needed and decrease dose by one dose level.
Confusion or mood alteration \geq Grade 2	Withhold dose until symptoms resolve. When dose restarted, decrease dose by one dose level.
Muscle weakness (steroid myopathy) \geq Grade 2	Withhold dose until muscle weakness \leq Grade 1. When dose restarted decrease dose by one dose level.

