Hyperglycemia \geq Grade 3	Decrease dose by one dose level. Treat with insulin or oral hypoglycemic agents as needed.
Acute pancreatitis	Discontinue subject from Dex treatment regimen.
Other \geq Grade 3 Dex-related adverse Events	Stop Dex dosing until the adverse event resolves to \leq Grade 2. Decrease by one dose level when Dex dosing is resumed.

^a If recovery from toxicities is prolonged beyond 14 days, then the dose of Dex will be decreased by one dose level when dose is restarted.

Table 7: Dexamethasone Dose Reduction Steps

Dose Level	≤ 75 years old	>75 years old
Starting Dose	40 mg	20 mg
Dose Level -1	20 mg	12 mg
Dose Level -2	10 mg	8 mg

ATRA will be administered in a divided dose of twice daily as an oral formulation at 35 mg/m²/day for Phase with dose escalation to 45mg/m²/day for 3 days. The dose expansion phase will be at the 45 mg/m²/day dose after safety and efficacy has been evaluated. The first administration of ATRA will be given in the morning, two days before the scheduled Dara infusion. The last administration of ATRA will be given in the evening of the day that Dara was administered (days -2, -1, and 1; day 1 is the day of Dara infusion).

ATRA-related toxicities

Subjects will be monitored for neurological symptoms and nutritional status. If Wernicke's encephalopathy is suspected, ATRA should be interrupted and parenteral thiamine should be initiated.

Pseudotumor cerebri

This complication has been mainly reported in patients aged <20 years and is characterized by presence of severe headache with nausea, vomiting, and visual disorders.

It is recommended to temporarily discontinue ATRA treatment and to administer opiates. As soon as the symptoms and the patient clinical conditions improve, the treatment with ATRA will be resumed at 50% of the previous dose during the first 7 days after the amelioration of pseudotumor cerebri. Thereafter, in absence of worsening of the previous toxicity, ATRA should be resumed at full dosage.

Table 8: ATRA Dose Reduction Steps

Dose Level	ATRA Dose reduction
Dose Level 2	45 (mg/m ²)
Dose Level 1 (Phase 1b starting dose)	35.5 (mg/m ²)
Dose Level -1	25 (mg/m ²)
Dose Level -2	20 (mg/m ²)

- ATRA will be discontinued for any Grade 4 non-hematologic toxicity.
- In the case of Grade 3 toxicity, ATRA should be held until the toxicity resolves to Grade ≤ 1 or baseline, at which time it may be resumed at a reduced dose.

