7.6. Criteria for Discontinuing ATRA and Discontinuation from Study

ATRA should be discontinued in patients experiencing an AE in Cycle 1 meeting criteria for a DLT for which the investigator considers that retreatment of the patient could be dangerous. For Grade 4 life threatening TEAEs, the subject will be permanently withdrawn from study, except when the investigator determines that the patient is receiving clinical benefit and there are chances to provide supportive care to mitigate the Grade 4 event to recur. In these circumstances, treatment may be restarted at the previously safe dose level or below when toxicity recovers to Grade ≤ 1 or baseline.

If the next cycle of treatment is delayed for > 21 days because of ATRA-related toxicities, then the patient should have study treatment discontinued unless the investigator considers that the patient will receive benefit continuing in the study. If treatment discontinuation is determined, the end of study visit should be completed within 30-40 days after the last administration of ATRA.

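### The synopsis and Section 4.1 open phase 1b cycles after Cycle 1 to patients without a DLT, while Section 7.6 implies that some DLT patients are retreated, so the TEAE-discontinuation count depends on the section followed.

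*Combined protocol and SAP*

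**What the plan says.** **Continuation.** Section 4.1 says that, in dose escalation and after the first cycle, further cycles are available to "patients who have not experienced a DLT, have not shown signs of PD, and in the opinion of the investigator would continue to benefit". The synopsis (Study Design) carries the same condition and points to Section 7.4 for details. Section 7.4 sets out cohort sizes, escalation, expansion and replacement. It does not say what happens to a patient who has had a DLT.

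**Stopping.** Section 7.6 says "ATRA should be discontinued in patients experiencing an AE in Cycle 1 meeting criteria for a DLT for which the investigator considers that retreatment" could be dangerous. It also ends study treatment after a delay of more than 21 days due to ATRA-related toxicity, "unless the investigator considers that the patient will receive benefit continuing in the study".

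**What counts as a DLT.** For Cycle 1 events clearly unrelated to the underlying disease, Section 7.3 lists "Grade 4 thrombocytopenia of any duration", Grade 4 neutropenia beyond 7 days, and most non-hematologic events of Grade 3 or higher. A delay of Cycle 2 by more than 3 weeks through incomplete recovery from treatment-related toxicity is also a DLT.

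**Resumption.** For pomalidomide after Grade 4 thrombocytopenia, Table 4 in Section 7.5 says "Dosing may resume at one dose level lower once the platelet count has recovered". For ATRA, Section 7.5 says "In the case of Grade 3 toxicity, ATRA should be held until the toxicity resolves", after which a reduced dose may be given. Section 7.5 also restarts daratumumab after recovery.

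**Endpoint.** Section 3 lists "Patients who discontinue because of TEAEs" and patients with dose modifications (delays, interruptions or reductions) as separate components of the phase 1b primary endpoint, reported overall and per dose level.

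**The concern.** A no-DLT condition on further cycles has a purpose only if patients with a DLT do not get them. The qualifier in Section 7.6 has a purpose only if some of them do. Both texts cover the same patients in the same cycle, and nothing ranks one above the other.

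At stake is a listed component of the phase 1b primary endpoint in very small cohorts. A patient whose DLT resolves is a discontinuation because of a TEAE under one text and need not be under the other. The choice also decides whether that patient contributes later-cycle exposure and later adverse events. Section 7.3 uses DLT-like events in later cycles to judge whether the MTD dose suits future studies, so this reaches beyond bookkeeping.

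**Working it through.** **1. Rules side by side, for an event that is a Cycle 1 DLT under Section 7.3**

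| Cycle 1 event | Synopsis and 4.1 | Other text |
|---|---|---|
| Any DLT | No route to Cycle 2 on the natural reading | 7.6: ATRA stops only if retreatment is judged dangerous |
| Grade 4 thrombocytopenia | Same | Table 4: pomalidomide withheld, then resumed one level lower |
| Grade 3 non-hematologic event, not excepted | Same | 7.5: ATRA held, then may resume at a reduced dose |
| Cycle 2 delayed by more than 3 weeks | Same | 7.6: may continue if the investigator sees benefit (ATRA-related delay) |

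The first row is the direct conflict, because Section 7.6 names Cycle 1 DLTs. The others are general rules for all cycles and for phase 2. They conflict only because Cycle 1 of phase 1b is not carved out, and Section 7.3 itself sends the reader to Section 7.5 for dose modifications.

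**2. Effect on the endpoint.** Take a Cycle 1 Grade 4 thrombocytopenia that recovers. Pomalidomide withheld during scheduled dosing is an interruption, so the patient counts as a dose modification under either text. Under 4.1 the patient also counts as a discontinuation because of a TEAE; under Table 4 the patient does not. Only the discontinuation count moves. DLTs are counted before Cycle 2 Day 1, so the DLT count and the MTD decision are the same either way.

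**3. How many patients could be affected.** Inputs are the 3+3 rules of Section 7.4: cohorts of 3, one DLT in 3 expands to 6, two or more stop escalation, and the lower level is filled to 6 if the level above exceeds the MTD. Enumerating all paths gives 3 to 12 patients, which reproduces the range in Section 9.2 (replacements not counted). At most 7 of 12 can have a DLT: 1 + 3 at level 2, then 3 in the back-fill of level 1.

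The documents give no DLT probability p, so I assume the same p at both levels, from 10% to 40%. The main case fills level 2 to 6, because Section 7.4 defines the MTD on a cohort of 6.

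Let q = 1 − p, A0 = q³ and A1 = 3pq². Then

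E[n] = 3 + 3·A1 + (A0 + A0·A1)·(3 + 3(A0 + A1)) + 3·A0·(1 − q⁶ − 6pq⁵).

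At p = 0.2, A0 = 0.512 and A1 = 0.384, so E[n] = 3 + 1.152 + 0.7086 × 5.688 + 1.536 × 0.3446 = 8.71. The expected number with a DLT is p × E[n] = 0.2 × 8.71 = 1.74.

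The chance of at least one DLT is 1 − q⁹, since a DLT-free phase 1b is 0/3 then 0/6. It is 1 − q⁶ if level 2 stops after 0/3. At p = 0.2 these are 1 − 0.134 = 0.866 and 1 − 0.262 = 0.738.

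| Assumed p | Expected treated | Expected with a DLT | P(at least one) | P(at least one), level 2 not filled after 0/3 |
|---|---|---|---|---|
| 10% | 9.3 | 0.9 | 61% | 47% |
| 20% | 8.7 | 1.7 | 87% | 74% |
| 30% | 7.6 | 2.3 | 96% | 88% |
| 40% | 6.3 | 2.5 | 99% | 95% |

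The first three result columns are for level 2 filled to 6.

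**4. Shift per patient.** In a cohort of 6, one patient is 1/6 = 17 percentage points of the discontinuation rate. A single DLT in a cohort of 3 always leads to expansion to 6, so 1/3 = 33 points is not a final figure for a lone DLT.

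**The case against.** The best defence is that Section 4.1 is permissive. It says who may continue and does not say that a patient with a DLT must stop. Section 7.6 is the section on discontinuation and can be read as governing, with the synopsis and 4.1 as summary. A reader might infer that 4.1 expressly bars treatment after a DLT. It does not; that is the natural reading rather than the literal text. What survives is that the no-DLT condition does no work on the permissive reading, and no section says that 7.6 prevails.

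A reader might also infer that an affected patient moves from one endpoint component to the other. Section 3 does not make the two exclusive, and a withheld dose is already an interruption, so this is not supported.

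Nor do the documents support saying that the two sites' counts could not be combined. The study team reviews all treated patients before each escalation and documents its decisions (Section 7.4), and monthly teleconferences are planned (Section 11.3). These arrangements make divergence easier to catch, but they do not say which rule to apply.

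Finally, not every DLT patient would resume under Sections 7.5 and 7.6. ATRA stops for Grade 4 non-hematologic toxicity in 7.5, Table 4 ends study treatment for Grade 4 rash, and 7.6 stops ATRA where retreatment is judged dangerous. The 17 points is therefore an upper bound per patient.

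**Conclusion.** The inconsistency is real and should be corrected. It rests mainly on the synopsis and Section 4.1 against the first sentence of Section 7.6; Section 7.5, Table 4 and the 21-day override add to it because they contain no phase 1b exception. It leaves undefined whether a patient with a Cycle 1 DLT is treated further, and with that the TEAE-discontinuation count, later-cycle exposure and later DLT-like events.

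Under an assumed common DLT probability of 10% to 40%, at least one such patient is more likely than not with level 2 filled to 6 (61% to 99%), and 47% to 95% likely otherwise. Each can move the discontinuation rate by up to 17 points in a cohort of 6.

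A reader might infer that dose selection or the phase 2 test is compromised. It is not: the DLT count, the 3+3 MTD decision and the Simon design are untouched. A reader might also size the problem on a fixed 12 patients. Twelve is the maximum, and 3+3 stopping brings the expected number treated to between 6.3 and 9.3 over the assumed range.

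**What to change.** Reconcile the synopsis and Section 4.1 with Sections 7.5 (including Table 4) and 7.6, so that one rule says whether a patient with a Cycle 1 DLT may receive further cycles. State it once and cross-refer to it elsewhere, including from Section 7.4, where the synopsis now sends the reader. Which clinical rule to adopt is the sponsor's decision.

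In Section 3 or the analysis plan, state that discontinuation because of a TEAE and dose modification are counted separately and are not mutually exclusive, and tabulate both by dose level.

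The cost is protocol wording in an amendment, with no added patients, visits or procedures.
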